## 10.8. Appendix 8: Hypersensitivity Event Tests

This table lists the recommended tests that should be obtained in case of a clinically significant hypersensitivity/allergy event. Selected tests may be obtained in the event of anaphylaxis or generalized urticaria.

Anti-LY antibodies (immunogenicity)	Tryptase
LY concentration (PK)	N-methylhistamine
	Drug-specific IgE a
	Basophil activation test a
	Complements
	Cytokine panel

Abbreviations: Ig = immunoglobulin; LY = LY3493269; PK = pharmacokinetics.

a Basophil activation test will be performed if a drug-specific IgE assay is unavailable.

## **10.9. Appendix 9: Provisions for Changes in Study Conduct during Exceptional Circumstances**

### **Implementation of this appendix**

The changes to procedures described in this appendix are temporary measures intended to be used only during specific time periods as directed by the sponsor in partnership with the investigator.

#### **Exceptional circumstances**

Exceptional circumstances are rare events that may cause disruptions to the conduct of the study. Examples include pandemics or natural disasters. These disruptions may limit the ability of the investigators, participants, or both to attend on-site visits or to conduct planned study procedures.

#### **Implementing changes under exceptional circumstances**

In an exceptional circumstance, after receiving the sponsor's written approval, sites may implement changes if permitted by local regulations.

After approval by local ethical review boards, regulatory bodies and any other relevant local authorities, implementation of these exceptional circumstance changes will not typically require additional notification to these groups, unless they have specific requirements in which notification is required (for example, upon implementation and suspension of changes). All approvals and notifications must be retained in the study records.

If the sponsor grants written approval for changes in study conduct, the sponsor will also provide additional written guidance, if needed.

#### **Considerations for making a change**

The prevailing consideration for making a change is ensuring the safety of study participants. Additional important considerations for making a change are compliance with GCP, enabling participants to continue safely in the study and maintaining the integrity of the study.

#### **Informed consent**

Additional consent from the participant will be obtained, if required, for

- participation in remote visits, as defined in Section “Remote Visits,”
- provision of their personal or medical information required prior to implementation of these activities.

#### **Changes in study conduct during exceptional circumstances**

Changes in study conduct not described in this appendix, or not consistent with applicable local regulations, are not allowed.

The following changes in study conduct will not be considered protocol deviations.

### **Remote visits**

Telephone- or technology-assisted virtual visits, or both, are acceptable to complete appropriate assessments. Assessments to be completed in this manner include, but are not limited to, review of AEs and concomitant medications.

#### *Data capture*

In source documents and the CRF, the study site should capture the visit method, with a specific explanation for any data missing because of missed in-person site visits.

#### *Safety reporting*

Regardless of the type of remote visits implemented, the protocol requirements regarding the reporting of AEs, SAEs, and product complaints remain unchanged.

#### *Return to on-site visits*

Every effort should be made to enable participants to return to on-site visits as soon as reasonably possible, while ensuring the safety of both the participants and the site staff.

### **Screening period guidance**

To ensure safety of study participants, laboratory values and other eligibility assessments taken at the screening visit are valid for a maximum of 28 days. The following rules will be applied for active, non-enrolled participants whose participation in the study must be paused due to exceptional circumstances:

#### *Adjustments to visit windows*

Whenever possible and safe to do so, as determined by the investigator's discretion, participants should complete the usual SoA. Allowable visit interval tolerance limits are included in the SoA (Section 1.3). To maximize the possibility that these visits can be conducted as on-site visits, the windows for visits may be adjusted, upon further guidance from the sponsor. This minimizes missing data and preserves the intended conduct of the study.

### **Documentation**

#### *Changes to study conduct will be documented*

Sites will identify and document the details of how participants, visit types, and conducted activities were affected by exceptional circumstances.

*Source documents at alternate locations*

Source documents generated at a location other than the study site should be part of the investigator's source documentation and should be transferred to the site in a secure and timely manner.

## 10.10. Appendix 10: Abbreviations and Definitions

---

Term	Definition
ADA	Antidrug antibody
AE	adverse event
ALT	alanine aminotransferase
ALP	alkaline phosphatase
AST	aspartate aminotransferase
AUC	area under the concentration versus time curve
BP	Blood pressure
C10	sodium caprate
CI	confidence interval
Cmax	maximum observed drug concentration
companion diagnostic	An in vitro diagnostic device (assay or test) that provides information that is essential for the safe and effective use of a corresponding therapeutic product
complaint	A complaint is any written, electronic, or oral communication that alleges deficiencies related to the identity, quality, purity, durability, reliability, safety or effectiveness, or performance of a drug or drug delivery system.
compliance	Adherence to all study-related, good clinical practice (GCP), and applicable regulatory requirements.
CRF	case report form; a printed, optical, or electronic document designed to record all of the protocol-required information to be reported to the sponsor for each trial participant.
CRP	clinical research physician: Individual responsible for the medical conduct of the study. Responsibilities of the CRP may be performed by a physician, clinical research scientist, global safety physician, or other medical officer.
CRU	clinical research unit
CT	computed tomography
CV	cardiovascular
ECG	Electrocardiogram
enroll	The act of assigning a participant to a treatment. Participants who are enrolled in the study are those who have been assigned to a treatment.
enter	Participants entered into a study are those who sign the informed consent form directly or through their legally acceptable representatives.

GCP	good clinical practice
GI	gastrointestinal
GIP	glucose-dependent insulinotropic polypeptide
GLP	glucagon-like peptide
GZHA	Study J1X-MC-GZHA
GZHB	Study J1X-MC-GZHB
GZHC	Study J1X-MC-GZHC
GZHF	Study J1X-MC-GZHF
GZHI	Study J1X-MC-GZHI
HR	Heart rate
IB	Investigator's Brochure
ICF	informed consent form
ICH	International Council for Harmonisation
IEC	independent ethics committee
informed consent	A process by which a participant voluntarily confirms their willingness to participate in a particular study, after having been informed of all aspects of the study that are relevant to the participant's decision to participate. Informed consent is documented by means of a written, signed, and dated informed consent form.
investigational product	A pharmaceutical form of an active ingredient or placebo being tested or used as a reference in a clinical trial, including products already on the market when used or assembled (formulated or packaged) in a way different from the authorized form, or marketed products used for an unauthorized indication, or marketed products used to gain further information about the authorized form.
IP	investigational product
IRB	institutional review board
NASH	nonalcoholic steatohepatitis
participant	Equivalent to CDISC term "subject": an individual who participates in a clinical trial, either as recipient of an investigational medicinal product or as a control
PK/PD	pharmacokinetics/pharmacodynamics
QTcF	QT interval corrected using Fridericia's formula
RA	receptor agonist

SAE	serious adverse event
SC	subcutaneous
screen	The act of determining if an individual meets minimum requirements to become part of a pool of potential candidates for participation in a clinical study.
SNAC	salcaprozate sodium
SoA	Schedule of activities
T2DM	type 2 diabetes mellitus
TBL	total bilirubin level
TE	treatment emergent
treatment-emergent adverse event	An untoward medical occurrence that emerges during a defined treatment period, having been absent pretreatment, or worsens relative to the pretreatment state, and does not necessarily have to have a causal relationship with this treatment.
ULN	upper limit of normal
WNOCBP	Women not of childbearing potential

## 2. ABBREVIATIONS

Abbreviations pertain to the Statistical Analysis Plan (SAP) only (not the tables, figures and listings [TFLs]).

%AUC( $t_{last}-\infty$ )	Percentage of AUC(0- $\infty$ ) extrapolated
ADA	Anti-drug antibody
AE	Adverse event
AESI	Adverse events of special interest
ALP	Alkaline phosphatase
ALT	Alanine aminotransferase
AUC	Area under the concentration versus time curve
AUC(0- $\infty$ )	area under the concentration versus time curve from time zero to infinity
AUC(0- $t_{last}$ )	Area under the concentration versus time curve from time zero to time $t$ , where $t$ is the last time point with a measurable concentration
AUC $_{\tau}$	Area under the concentration versus time curve during one dosing interval
BQL	Below the quantifiable lower limit of the assay
C10	Sodium caprate
CI	Confidence interval
CL/F	Apparent total body clearance of drug calculated after extra vascular administration
C last	Last quantifiable drug concentration
C max	Maximum observed drug concentration
C min	Minimum observed drug concentration
CRF	Case Report Form
CRU	Clinical Research Unit
CSR	Clinical Study Report
CV	Coefficient of variation
DMP	Data Management Plan
EC	Early Clinical
ECG	Electrocardiogram
F Abs	Absolute bioavailability of each oral treatment compared to an intravenous formulation

---

$F_{\text{Rel}}$	Relative bioavailability of the test formulation compared to reference formulation
ICH	International Conference on Harmonisation
LLOQ	Lower limit of quantification
MedDRA	Medical Dictionary for Regulatory Activities
MRE	Magnetic resonance elastography
PK	Pharmacokinetic
$R_A$	Accumulation ratio
SAP	Statistical Analysis Plan
SD	Standard deviation
SNAC	Salcaprozate sodium
SOP	Standard Operating Procedure
$t_{1/2}$	Half-life associated with the terminal rate constant ( $\lambda_z$ ) in non-compartmental analysis
TBL	Total bilirubin
TEADAs	Treatment-emergent anti-drug antibody
TEAEs	Treatment-emergent adverse event
TFLs	Tables, Figures, and Listings
$t_{\text{last}}$	Time of the last quantifiable concentration
$t_{\text{max}}$	Time of maximum observed drug concentration
ULN	Upper limit of normal
$V_{\text{ss/F}}$	Apparent volume of distribution at steady state after extra-vascular administration
$V_z/F$	Apparent volume of distribution during the terminal phase after extra-vascular administration
WHO	World Health Organization

### 3. INTRODUCTION

This SAP has been developed after review of the Clinical Study Protocol (final version dated 18 September 2022).

This SAP describes the planned analysis of the safety, tolerability and pharmacokinetic (PK) data from this study. A detailed description of the planned TFLs to be presented in the clinical study report (CSR) is provided in the accompanying TFL shell document.

The intent of this document is to provide guidance for the statistical and PK analyses of data. In general, the analyses are based on information from the protocol, unless they have been modified by agreement with Eli Lilly and Company. A limited amount of information concerning this study (e.g., objectives, study design) is given to help the reader's interpretation. This SAP must be finalized prior to first participant visit. When the SAP and TFL shells are agreed upon and finalized, they will serve as the template for this study's CSR.

This SAP supersedes the statistical considerations identified in the protocol; where considerations are substantially different, they will be so identified. If additional analyses are required to supplement the planned analyses described in this SAP, they may be performed and will be identified in the CSR. Any substantial deviations from this SAP will be agreed upon with Eli Lilly and Company and identified in the CSR. Any minor deviations from the TFLs may not be documented in the CSR.

This SAP is written with consideration of the recommendations outlined in the International Conference on Harmonisation (ICH) E9 Guideline entitled Guidance for Industry: Statistical Principles for Clinical Trials and the ICH E3 Guideline entitled Guidance for Industry: Structure and Content of Clinical Study Reports.

### 4. STUDY OBJECTIVES AND ENDPOINTS

Objectives	Endpoints
Primary	

To evaluate and compare the PK of up to 3 test capsule formulations with a reference tablet formulation of LY3493269 following 3 consecutive once-daily oral doses in healthy participants

 

Area under the concentration versus time curve (AUC) and maximum observed drug concentration (<math>C_{max}</math>)

Secondary	

To evaluate the PK of up to 2 LY3493269 formulations when administered in a fed condition following 3 consecutive once-daily oral doses in healthy participants

 

AUC and <math>C_{max}</math>

To assess the safety and tolerability of up to 3 test capsule formulations of LY3493269 with that of a reference tablet formulation following 3 once-daily oral doses in healthy participants

	

Treatment-emergent adverse events (TEAEs)

Exploratory	

To assess PK of salcaprozate sodium (SNAC) and sodium caprate (C10) following oral administration in healthy participants

	

AUC and <math>C_{max}</math>

## 5. STUDY DESIGN

This is a 2-part, open-label study with a parallel design to be conducted in healthy participants.

The purpose of this study is to evaluate and compare the PK of up to 3 test capsule formulations with a reference tablet formulation of LY3493269 following 3 consecutive once-daily oral doses in healthy participants.

Study details include:

- The study duration will be up to 71 days.
- The treatment duration involves consecutive once-daily dosing up to 3 days.
- The visit frequency will be one inpatient stay (Day -1 through Day 5) and 5 outpatient visits.

In Parts A and B, eligible participants will receive 3 once-daily doses of study intervention.

The maximum total duration of study participation for each participant may be up to 71 days, across the following study intervals:

- Screening, approximately 28 days
- Study period, approximately 15 days, and
- Follow up, approximately 28 days after the last dose of study intervention.

The study shall target 10 participants completing each treatment – that is, these participants must complete Day 8 PK assessments after receiving all 3 consecutive daily doses of the study treatment.

### Part A

Part A of the study is an initial characterization of 2 test capsule formulations, compared with a reference tablet formulation. Participants will be randomly assigned to receive 1 of the 3 possible treatments as follows:

- Treatment A1: Test capsule formulation 1
- Treatment A2: Test capsule formulation 2
- Treatment A3: Reference tablet formulation

---

Test formulations 1 and 2 and the reference formulation will be administered in the fasted state.

## **Part B**

Part B of the study will investigate the test capsule formulations 1, 2, or 3 or the reference tablet formulation.

An initial review of safety and PK data from Part A will be conducted to determine the test or reference formulation(s) to be evaluated in Part B. Participants will be assigned to 1 of the 2 possible treatments as follows:

- Treatment B1: Test formulations 1, 2, or 3 (referred to as “X” from this point forward)
- Treatment B2: Test formulations 1, 2, or 3 or reference formulation (referred to as “Y” from this point forward).

The 3 test formulations will be administered in either the fasted or fed state depending on the review of safety and PK data from Part A. If the reference formulation is selected as Treatment B2, it will be administered in the fasted state.

Depending on the review results, the selected formulation(s) will be administered in either the fed or fasted state.

Treatments B1 and B2 may be initiated concurrently if the formulations “X” and “Y” and administration conditions are determined for both treatment groups after the first review. Otherwise, a second review of available PK data from Treatment B1 may be conducted prior to the initiation of Treatment B2.

## **Changes from the Planned Study Design**

At the time of writing this SAP amendment, the Sponsor has decided not to proceed with Part B of the study. All further references to Part B are no longer applicable.

## **6. BLINDING**

This is a randomized, open-label study.

The Fortrea biometrics and Eli Lilly study teams will be unblinded throughout the study.

## **7. TREATMENTS**

The following is a list of the study treatment labels that will be used in the TFLs. Where the abbreviation is used, the TFLs will include a footnote.

Part	Study Treatment Name	Abbreviation	Treatment order in TFLs
A	Test capsule 1: 4 mg LY3493269 + 280 mg C10 (fasted)	A1	1
	Test capsule 2: 4 mg LY3493269 + 280 mg C10 (fasted)	A2 {Insert brief description of indication}	2
	Reference tablet: 4 mg LY3493269 + 300 mg SNAC (fasted)	A3	3
B	Test capsule X: 4 mg LY3493269 + 280 mg C10 (TBC)	B1	4
	TBC Y: 4 mg LY3493269 + TBC (TBC)	B2	5

Abbreviations: C10 = sodium caprate; SNAC = salcaprozate sodium; TBC = to be confirmed.

“X” can be test formulations 1, 2 or 3; “Y” can be test formulations 1, 2, 3 or reference formulation; The 3 test formulations will be administered in either the fasted or fed state depending on the review of safety and PK data from Part A. If the reference formulation is selected as Treatment B2, it will be administered in the fasted state. All TFLs will be based on actual treatments.

## 8. SAMPLE SIZE JUSTIFICATION

Up to approximately 70 participants may be randomly assigned to study intervention to ensure approximately 10 evaluable participants from each of the 5 planned treatment groups complete the study. **CCI**

Participants who are randomly assigned but not administered treatment prior to discontinuation may be replaced to ensure that the target number of participants complete the study.

Participants who discontinue early may be replaced after consultation with the investigator and sponsor. The replacement participant will be assigned to the same treatment as the discontinued participant.

## 9. DEFINITION OF ANALYSIS POPULATIONS

The “Entered” population will consist of all participants sign the informed consent form.

The “Randomized/Enrolled” population will consist of all participants assigned to treatment, regardless of whether they take any doses of study treatment, or whether they took the correct treatment. Participants will be analyzed according to the treatment group to which they were assigned.

The “Safety” population will consist of all enrolled participants who received at least one dose of LY3493269. Participants will be analyzed according to the intervention they actually received.

The “Pharmacokinetic” population will consist of all enrolled participants who received at least one dose of LY3493269 and have at least 1 evaluable PK sample.

All protocol deviations that occur during the study will be considered for their severity/impact and will be taken into consideration when participants are assigned to analysis populations.

## **10. STATISTICAL METHODOLOGY**

### **10.1 General**

Data listings will be provided for all data that is databased. Summary statistics and statistical analysis will only be presented for data where detailed in this SAP. For continuous data, summary statistics will include the arithmetic mean, arithmetic standard deviation (SD), median, minimum, maximum and number of observations; for log-normal data (e.g. the PK parameters: AUC and  $C_{\max}$ ) the geometric mean and geometric coefficient of variation (CV%) will also be presented. For categorical data, frequency count and percentages will be presented. Data listings will be provided for all participants up to the point of withdrawal, with any participants excluded from the relevant population highlighted. Summary statistics and statistical analyses will generally only be performed for participants included in the relevant analysis population. For the calculation of summary statistics and statistical analysis, unrounded data will be used.

For change from baseline summary statistics, each individual change from baseline will be calculated by subtracting the individual participant’s baseline value from the value at that time point. The individual participants’ change from baseline values will be used to calculate the summary statistics (arithmetic mean, arithmetic SD, median, minimum, maximum and number of observations) using a SAS procedure such as Proc Univariate.

Data analysis will be performed using SAS® Version 9.4 or greater.

### **10.2 Demographics and Participant Disposition**

Participant disposition will be summarized and listed. The demographic variables age, sex, race, ethnicity, country of enrolment, site ID, body weight, height and body mass index will be summarized and listed. All other demographic variables will be listed only.

### **10.3 Pharmacokinetic Assessment**

#### **10.3.1 Pharmacokinetic Analysis**

Noncompartmental methods applied with a validated software program (Phoenix WinNonlin v8.3.5) to the plasma concentrations of LY3493269, SNAC, and C10 will be used to determine the following PK parameters in Parts A and B, when possible:

### Profile Day 1

Parameter	Units	Definition
AUC(0-t last )	ng.h/mL	area under the concentration versus time curve from time zero to time t, where t is the last time point with a measurable concentration
AUC τ	ng.h/mL	area under the concentration versus time curve during one dosing interval
C max	ng/mL	maximum observed drug concentration
t max	h	time of maximum observed drug concentration
t last	h	time of the last quantifiable concentration

### Profile Day 2

Parameter	Units	Definition
AUC(0-t last )	ng.h/mL	area under the concentration versus time curve from time zero to time t, where t is the last time point with a measurable concentration
AUC τ,day 2	ng.h/mL	area under the concentration versus time curve during one dosing interval at day 2
C max,day 2	ng/mL	maximum observed drug concentration
t max,day 2	h	time of maximum observed drug concentration
t last	h	time of the last quantifiable concentration

### Profile Day 3

Parameter	Units	Definition
AUC(0-t last )	ng.h/mL	area under the concentration versus time curve from time zero to time t, where t is the last time point with a measurable concentration
AUC τ,day 3	ng.h/mL	area under the concentration versus time curve during one dosing interval at day 3
AUC(0-∞)	ng.h/mL	area under the concentration versus time curve from time zero to infinity
%AUC(t last -∞)	%	percentage of AUC(0-∞) extrapolated
C max,day 3	ng/mL	maximum observed drug concentration
t max,day 3	h	time of maximum observed drug concentration
t last	h	time of the last quantifiable concentration
t ½	h	half-life associated with the terminal rate constant (λz) in non-compartmental analysis
CL/F	L/h	apparent total body clearance of drug calculated after extra-vascular administration
V Z/F	L	apparent volume of distribution during the terminal phase after extra-vascular administration
V ss/F	L	apparent volume of distribution at steady state after extra-vascular administration
R A	none	accumulation ratio (based on AUC τ on Profile Days 1 and 3)
F Rel	%	relative bioavailability of the test formulation compared to reference formulation (based on AUC[0-∞])
F Abs	%	absolute bioavailability of each oral treatment compared to an intravenous formulation (based on dose-normalized [DN] AUC[0-∞]):
$F_{Abs} = \frac{\text{Oral DN}^a \text{ AUC}(0 - \infty)}{\text{IV}^b \text{ DN AUC}(0 - \infty)} \times 100$		

a derived by dividing by the total oral dose administered (12)

b obtained from study J1X-MC-GZHA, using the geometric mean AUC(0-∞) of CCI LY3493269 IV

Additional PK parameters may be calculated, as appropriate. The software and version used for the final analyses will be specified in the clinical study report. Any exceptions or special handling of data will be clearly documented within the final study report.

Formatting of tables, figures and abbreviations will follow the Eli Lilly Global PK/PD/TS Tool: NON-COMPARTMENTAL PHARMACOKINETIC STYLE GUIDE. The version of the tool effective at the time of PK analysis will be followed.

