## General PK Parameter Rules

- Actual sampling times will be used in the final analyses of individual PK parameters, except for non-bolus pre-dose sampling times which will be set to zero. For non-bolus, multiple dose profiles, the pre-dose time will be set to zero unless a time deviation falls outside of the protocol blood collection time window which is considered to impact PK parameter derivation.
- $C_{\max}$ ,  $C_{\max, \text{day } 2}$ ,  $C_{\max, \text{day } 3}$ ,  $t_{\max}$ ,  $t_{\max, \text{day } 2}$ ,  $t_{\max, \text{day } 3}$ , and  $t_{\text{last}}$  will be reported from observed values. On a given profile day, if  $C_{\max}$  occurs at more than one time point,  $t_{\max}$  will be assigned to the first occurrence of  $C_{\max}$ .
- AUC parameters will be calculated using a combination of the linear and logarithmic trapezoidal methods (linear-log trapezoidal rule). The linear trapezoidal method will be applied up to  $t_{\max}$  and then the logarithmic trapezoidal method will be used after  $t_{\max}$ . The minimum requirement for the calculation of AUC will be the inclusion of at least three consecutive plasma concentrations above the lower limit of quantification (LLOQ), with at least one of these concentrations following  $C_{\max}$ . AUC(0- $\infty$ ) values where the percentage of the total area extrapolated is more than 20% will be flagged. Any AUC(0- $\infty$ ) value excluded from summary statistics will be noted in the footnote of the summary table.
- Half-life ( $t_{1/2}$ ) will be calculated, when appropriate, based on the apparent terminal log-linear portion of the concentration-time curve. The start of the terminal elimination phase for each participant will be defined by visual inspection and generally will be the first point at which there is no systematic deviation from the log-linear decline in plasma concentrations. Half-life will only be calculated when a reliable estimate for this parameter can be obtained comprising of at least 3 data points. If  $t_{1/2}$  is estimated over a time window of less than 2 half-lives, the values will be flagged in the data listings. Any  $t_{1/2}$  value excluded from summary statistics will be documented in the footnote of the summary table.
- A uniform weighting scheme will be used in the regression analysis of the terminal log-linear portion of the concentration-time curve.

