### **10.3.2 Pharmacokinetic Statistical Methodology**

The PK parameters of LY3493269 will be evaluated to estimate the relative bioavailability. Log-transformed  $AUC_{\tau}$ ,  $AUC(0-t_{last})$ ,  $AUC(0-\infty)$  (profile day 3 only) and  $C_{max}$  of LY3493269 will be evaluated in a mixed model for repeated measures with fixed effects for treatment, profile day and the treatment-by-day interaction, and a random effect for participant. An unstructured covariance structure will be used to model the covariance between a participant's multiple observations, with an alternative structure to be used if the model fails to converge. The geometric least squares means, ratio of geometric least squares means and corresponding 90% CI will be reported.

One model including all treatments (A1, A2, A3, B1 and B2) will be used to present the following comparisons for each profile day:

- Test capsule X versus Reference tablet, where X=1, 2 or 3.
- Fed versus fasted, for matching formulation.
- 240 mL versus 120 mL water administration, for matching formulation and dietary status.

Example SAS code:

```
proc mixed data=xxxx;
  by param;
  class treat day subjid;
  model lpk = treat day treat*day / residual ddfm=kr2;
  repeated day / subject=subjid type=un;
  lsmeans treat*day / cl pdiff alpha=0.1;
  ods output lsmeans=lsm diff=dif;
run;
```

The parameter  $t_{max}$  of LY3493269 will be analyzed non-parametrically. Estimates of the median difference, approximate 90% CI and p-value from the Wilcoxon rank sum test will be calculated.

All PK parameters will be summarized using descriptive statistics.

Additional analysis may be conducted if deemed necessary.

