## 15. APPENDICES

### Appendix 1: Document History

Status and Version	Date of Change	Summary/Reason for Changes
Final Version 1.0	NA	NA; the first version.
Final Version 2.0	30JUN2023	
Added additional PK parameter, <math>F_{Abs}</math>, following request from Sponsor.
 
<math>AUC(0-\infty)</math> on profile day 3 added to statistical analysis following request from Sponsor.
 
Part B of the study has been cancelled – text added to Sections 5 and 12 to clarify.
 
“Labcorp Drug Development” amended to “Fortrea” throughout.

NA = not applicable

Signature Page for VV-CLIN-123648 v1.0

Approval	PPD PKPDPMx 04-Jul-2023 13:18:29 GMT+0000
Approval	PPD Statistician 04-Jul-2023 13:26:07 GMT+0000
Approval	PPD PKPDPMx 05-Jul-2023 06:48:24 GMT+0000
Approval	PPD Statistician 05-Jul-2023 17:10:22 GMT+0000

Signature Page for VV-CLIN-123648 v1.0

Approved on 05 Jul 2023 GMT

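### As labelled, F_Abs divides a Day 3 AUC(0-∞), which on the plain reading starts at the third dose, by the total of all three doses, so absolute bioavailability would read low

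*SAP*

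**What the plan says.** SAP section 10.3.1 lists the pharmacokinetic parameters in three tables, one per profile day. AUC(0-∞) appears only in the Profile Day 3 table, defined as "area under the concentration versus time curve from time zero to infinity". The row does not say which dose is time zero. AUC(0-t_last) stands in all three daily tables and is also measured from time zero.

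F_Abs is a row of the same Day 3 table. It is the dose-normalised oral AUC(0-∞) over the dose-normalised intravenous AUC(0-∞), times 100. Footnote a says that the oral value is "derived by dividing by the total oral dose administered (12"; the bracket closes there without a unit. The intravenous value is a geometric mean from another study.

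Three other places bear on the window:

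- SAP section 10.3.2 models AUC(0-∞) for "profile day 3 only".
- The document history entry for Version 2.0, the version that added F_Abs, describes AUC(0-∞) "on profile day 3 added to statistical analysis following request from Sponsor".
- The accumulation ratio, also a Day 3 row, states that it is based on AUCτ "on Profile Days 1 and 3". The F_Abs row names no other day.

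**The concern.** A dose-normalised AUC is meaningful only if the AUC window and the dose cover the same administrations. Here the labels place the AUC on Day 3, while the divisor counts Days 1, 2 and 3. On that reading the numerator omits the first 48 h after dose 1 and the first 24 h after dose 2, but the divisor counts both doses in full.

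F_Abs is reported for each oral treatment against a fixed historical value, so nothing in the comparison cancels the mismatch: it passes straight into the reported percentage. A reader of the study report could not tell from the SAP which window was used.

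**Working it through.** **Inputs**

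- Dose per administration: 4 mg (Protocol section 6.1).
- Number of doses: 3, once daily, so 24 h apart (SAP section 5).
- Divisor: 12, no unit (SAP section 10.3.1, footnote a).
- Carry-over: subtraction of the pre-dose concentration is specified for C10 and SNAC only (Individual PK Parameter Rules). The Day 3 AUC of LY3493269 therefore keeps what remains of doses 1 and 2.
- Half-life t½ of LY3493269: not given. Assumed range 24 to 168 h.
- Further assumptions: linear kinetics, the same bioavailability for each dose, and absorption that is short compared with 24 h.

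**Reproducing the plan's figure.** 3 × 4 mg = 12 mg, which matches the printed 12.

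**Formula.** Let A be the AUC(0-∞) of one dose and e = 2^(-24/t½) the fraction remaining after 24 h.

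- AUC from dose 3 to infinity: all of dose 3, a fraction e of dose 2 and e² of dose 1, so A(1 + e + e²).
- AUC from dose 1 to infinity: 3A.
- The correct value per mg is 3A/12 = A/4.
- As labelled: A(1 + e + e²)/12. Ratio to truth: (1 + e + e²)/3.
- Day 3 AUC divided by 4 mg instead: ratio to truth 1 + e + e².

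Example at t½ = 24 h: e = 0.5, so (1 + 0.5 + 0.25)/3 = 1.75/3 = 0.583.

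| Assumed t½ (h) | e | Day 3 AUC / 12 mg, ratio to truth | Day 3 AUC / 4 mg, ratio to truth | Fraction of steady state after 3 doses, 1 - e³ |
|---|---|---|---|---|
| 24 | 0.500 | 0.583 | 1.75 | 0.875 |
| 48 | 0.707 | 0.736 | 2.21 | 0.646 |
| 72 | 0.794 | 0.808 | 2.42 | 0.500 |
| 120 | 0.871 | 0.876 | 2.63 | 0.340 |
| 168 | 0.906 | 0.909 | 2.73 | 0.257 |

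AUC from the first dose over 12 mg gives 1.00 in every row.

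**Checks**

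- Absorption: numerical integration of a one-compartment oral model with an assumed absorption rate of 1 per hour gives 0.591, 0.742, 0.812, 0.879 and 0.911 for the 12 mg column, so the simple formula is close.
- Unequal bioavailability by day: the estimate becomes (F3 + e·F2 + e²·F1)/3. Since e is below 1, this is below the mean of F1, F2 and F3. The direction does not depend on equal bioavailability or on the half-life.
- Size: F_Abs is low by less than 20% only if t½ exceeds about 69 h, and by less than 10% only if it exceeds about 152 h.
- Plausible half-lives: Protocol section 4.2 does not expect steady state after three days. The last column shows that this fits the longer half-lives better, where the bias is smaller.

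**The case against.** The best defence is that footnote a is the text most specific to F_Abs, and it deliberately counts all three doses. Paired with an AUC over the whole course, the formula is right. AUC(0-∞) can be completed only after the last dose, so its place in the Day 3 table, and the Day 3 labels elsewhere, may show only where it is reported. AUCτ, C_max and t_max carry a day 3 subscript in that table and AUC(0-∞) does not. The accumulation ratio has to name its days because AUCτ exists on several; AUC(0-∞) exists once. The General PK Parameter Rules say "For non-bolus, multiple dose profiles, the pre-dose time will be set to zero", but that governs sample times and does not define the origin of AUC(0-∞).

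This makes the whole-course reading possible, so a reader should not infer that F_Abs is certain to be biased. It does not make that reading the stated one. The missing subscript decides little, because AUC(0-t_last) also lacks one although it is reported separately for each day, with the same time-zero wording. No sentence in the SAP starts AUC(0-∞) at the first dose, and every day label attached to it says Day 3.

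A second objection is that noise exceeds the bias. With an assumed between-participant log-SD of 0.83 and 10 per group, the 90% interval for a group geometric mean runs from exp(-1.833 × 0.83/√10) = 0.62 to 1.62 times the estimate, and a shift of 9 to 12% would be hard to see. That is fair as to consequence, but a systematic mismatch in a stated formula is not excused by imprecision.

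A reader might also infer that the integration and below-quantification rules must be rewritten for a three-dose curve. The documents do not show this. The rule that ends a profile after consecutive unquantifiable values applies towards its end and allows an exception. The statement that "the logarithmic trapezoidal method will be used after" t_max is worded for one peak, which is a programming detail.

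**Conclusion.** The point holds in conditional form. On the labels as they stand, the window and the divisor of F_Abs do not match, and F_Abs is low by the factor (1 + e + e²)/3 at any finite half-life: about 0.58 at 24 h, 0.74 at 48 h, 0.88 at 120 h and 0.91 at 168 h. The direction is firm given linear kinetics. The size is not, because the documents give no half-life, and the upper end of that range is the more plausible. If AUC from the first dose was intended, the divisor of 12 mg is correct and the defect is an unstated window and a missing unit.

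A reader might infer that the trial's main comparison is affected. It is not: F_Abs is neither an objective nor an endpoint, and the primary AUC and C_max ratios and F_Rel do not use the divisor. It is worth correcting because the parameter was added at the sponsor's request and cannot be reproduced unambiguously from the SAP.

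**What to change.** In the F_Abs row and footnote a:

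- define the oral AUC(0-∞) as running from the first dose (Day 1 time zero) to infinity over all three doses;
- divide it by the total dose the participant actually received, which is 12 mg after three doses. The pharmacokinetic population requires only one dose, so a fixed 12 would not suit everyone in it;
- print the unit.

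If the first-dose window is already intended, the same wording settles the matter.

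The Day 3 AUC(0-∞) should not simply be divided by 4 mg. Carry-over from doses 1 and 2 would then bias F_Abs high, to 1.75 to 2.63 times truth at half-lives of 24 to 120 h.

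The cost is SAP wording and minor programming of the noncompartmental analysis. No new samples are needed, since the Schedule of Activities already samples all three dosing days and the decline after them.
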